All prisoners in the study undergo an oral examination to establish a baseline (hereafter T0) of oral health and a comprehensive questionnaire to identify risk factors and their attitude towards their oral health and oral treatment. Norwegian speaking prisoners are then randomized into either a treatment or control group. In the treatment group, dental staff initiate a conversation with the prisoner based on techniques from MI. Both groups finally receive a toilet bag with basic equipment to regularly clean their teeth. After 4 weeks and 12 weeks (hereafter T1 and T2), prisoners are invited back for another oral examination and a follow-up questionnaire, to measure changes in oral hygiene, oral cleaning routines, and attitude towards their oral health. At T1 we also conduct a screening of general learning difficulties using the validated screening tool HASI (Hayes, 2002). If the intervention proves to be an effective tool in improving oral hygiene, oral cleaning routines, and/or attitude towards own oral health, it can serve as an alternative proactive approach to improve oral health of a vulnerable group in society. If the improvements in oral hygiene and oral cleaning routines are long lasting, this may in turn lead to a reduced need of oral treatment. An improved attitude towards own oral health may, together with other rehabilitation programs in prison, improve the prisoner's self-esteem and chances to successfully returning to society after having served their prison sentence.

Study Design

Hypothesis:

H1: The conversation based on Motivating Interviewing (hereby the intervention) leads to a reduction in observed plaque and gingival inflammation for prisoners.

H2: The intervention leads to improved reported cleaning routines of prisoners in general, and particularly brushing of teeth.

H3: The intervention leads to a reduction in prisoners' intake of food and drinks in total, and particularly in-between meals.

H4: The intervention leads to improved perceptions about the prisoner's oral health. It improves how they view their oral health, they consider their oral health as more important, they report an increased wish to improve it, and they have increased efforts to improve it.

H5: The intervention leads to an increase in number of questions the prisoner asks during their visit with the dental staff, suggesting an increase in curiosity concerning their oral health.

Treatment effects and measurements:

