The main variable of interest and primary outcome measure of the treatment effect is the mucosal-plaque index (MPS). It consists of the sum of a four-point plaque score (PS) and a four-point mucosal score (MS). For the PS, score of 1 suggests no visible plaque, score of 2 suggests plaque is barely visible, score of 3 suggests a moderate amount of plaque, and score of 4 suggests large amount of plaque almost covering the whole surface of teeth. For the MS, score of 1 suggests normal mucosal, score of 2 suggests mild inflammation, score of 3 suggests medium inflammation, and score of 4 suggests strong inflammation. For both scores, if in doubt between 1 and 2, they are instructed to score 1. If in doubt between 3 and 4, they are instructed to score 4.

The index is designed to evaluate oral health and oral hygiene in groups of individuals, developed for use in institutions. This makes it a suitable index to be used when conditions are not optimal to assess the patient. In prison, dental staff have limited equipment and poor light compared to conditions at a dental clinic. It was therefore important to use an index designed to be used outside of dental clinics with less optimal conditions for oral examination.

The secondary measures of outcome are based on questionnaire responses. These are questions asked both prior to treatment and during the follow-up period, and measures changes in how the prisoner perceives his oral health, how his routines are for maintaining his teeth, and his intake of food and drinks. How these questions are formulated can be seen from the questionnaire directly. These questions are designed to measure behavioral changes because of the intervention. As the questions are identical at each meeting point, any difference in changes across the treatment and control group is likely to be a result of the intervention. Importantly, even though the MPS-index may not measure a significant change in oral hygiene, such behavioral changes may still be of great importance. For example, even though a prisoner does not change his cleaning routines and is unable to improve his plaque score, a reduction in intake of unhealthy food and drinks may still reduce the damage on his teeth. Likewise, an improved perception about their oral health, may still improve self-esteem, even though there is no reduction in plaque score.

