In addition, as a secondary outcome measure, dental staff take notes of how many times the prisoner asks questions about his teeth. If the intervention successfully increases the prisoner's interest in his own oral health, we could expect more questions about his oral health.

Basic methodology:

The study is a randomized control trial (RCT), testing an MI-based intervention on oral health (oral hygiene) for prisoners in Rogaland County, Norway. More details about the population and the intervention follows in subsequent sections.

We randomize prisoners into treatment or control groups, blocking at prison level, using the randomization tool at www.randomizer.org. See the randomization section for more details on the randomization process. Moreover, we blind prisoners from treatment status, and dental staff is either blind to treatment when doing the oral examinations, or the oral examination is conducted by two dental staff independently of each other. See the blinding section for more details on blinding.

Study design and procedures:

Geographic region

The geographic region of this study is Rogaland County in southwestern part of Norway. Rogaland County is the wealthiest county in Norway measured in terms of household income (2019, SSB). Despite being one of the wealthiest counties in Norway, growing up in Rogaland is similar to growing up in other counties in Norway. An important reason for this is the unitary and federally funded school system, with only a few ideological or pedagogical based private schools. This gives all children growing up in Norway similar opportunities to obtain an education and subsequently enter the labor market.

Research population

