The end date for data collection depends, in addition to uncertainty regarding whether additional funding is approved, on the extent that the ongoing pandemic will affect data collection. If stricter infection control measures are enforced, prisons are likely to quickly deny access for external partners. The new omicron variant of the corona virus has already forced delays in three out of four prisons. During a period in which we are not allowed to enter a prison, we will be forced to do follow-up examinations at times deviating from the times described above and our flow chart presented below. We are also likely to experience higher attrition during such periods, as prisoners are released or moved to a prison outside Rogaland County before we are allowed to do follow-up examinations. Such attrition is independent of treatment status. During periods we are not allowed to enter the prison, dental staff will work in their regular clinic instead. Therefore, we are not spending project resources during lockdowns.

During the data collection period we are aiming to recruit around 500 subjects. The number of subjects we can recruit depends on several factors. First, we rely on enough people serving their prison sentence during the data collection period. We know that prisons in Rogaland County have not been fully occupied in recent years. Second, the proportion of prisoners who choose to participate is uncertain. Third, time spent on each prisoner depends on how effectively the prison staff can bring prisoners to the examination room and how effective the routines of dental staff are. Forth, we do not know many of the prisoners have sufficient Norwegian language to participate in the study. See the power calculation section for a more detailed discussion about the required sample size.

[figure not shown]
Each prisoner is followed for 12 weeks in total, and we continuously recruit prisoners in the data collection period. The intervention occurs only at time T₀, and only for those randomized to the treatment group. During the first few months we recruit primarily those who are already imprisoned, and once all of them have been given the chance to participate, we start recruiting new prisoners.

Intervention

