The intervention is a conversation lasting up to 30 minutes with the prisoner about his or her oral health, based on Motivational Interviewing. The intervention is carried out by dental staff in prison. Prior to the start of data collection, dental staff has been trained by MI certified specialists from the Regional Alcohol and Drug Competence Center in Rogaland County. The training has consisted of three days of seminar with group work and discussions, a practice MI-conversation that has been recorded, transcribed, and graded by the MI-center in Bergen, and direct feedback on this practice conversation. In addition, they receive continuous guidance from a MI specialist at the Center for Alcohol and Drug Research at Stavanger University Hospital.

The MI conversation follows the methodology of MI closely. The first step is for the dental staff to ask open questions to the prisoner, for example “what cleaning routines do you have for your teeth?” or “what benefits could you get from brushing your teeth twice a day?”. The next step is to confirm to the prisoner what he or she is doing, for example “you are really trying hard to take good care of your teeth” or “you have managed to have good cleaning routines multiple times in the past”. The third step is called reflection. At this stage, dental staff tries to provide reflections on what the prisoner have said, for example by repeating what the prisoner have said or say the same using synonyms (simple reflection), by extracting the underlying opinion or feeling (complex reflection), or by illuminate both negative and positive sides of the situation (double sided reflection). The final step is to summarize the conversation. In addition, the intervention included a change plan, in which the prisoner and dental staff agrees on specific behavior that the prisoner should follow based on the MI conversation.

Include a flow chart:

Data collection and sources of data:

Data collection will be carried out by trained dental staff inside the prisons during the data collection period. Most data collected will be on individual (prisoner) level. Moreover, we will collect basic information about each of the four prisons in our study.

The source of data will be a combination of clinical information from the oral examination, answers from the questionnaire, and a few observations done by dental staff during the consultation.

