Prisoners are not informed whether they are in the treatment or control group and are therefore blind to treatment status. Dental staff are blind to prisoners' treatment status at the time of the first oral examination and questionnaire. The prisoner's treatment status is revealed just after this. Hence, dental staff collects all data prior to knowing the prisoner's treatment status, and only learn this when they start the MI-based conversation. When prisoners are back at T1 and T2 for follow-up oral examinations and questionnaires, dental staff might still remember whether the prisoner was treated or not. To partially account for potential bias in the oral examination (assessment of oral hygiene and inflammation in gingival), there are two independent assessments of this at T1 and T2. See pre-specification of analytical decisions for more on this.

Power calculations:

We have used GPower and Optimal Design to conduct power calculations.

GPower is used to calculate required sample size for simple comparison of means for the main variables of interest between the treatment and control group, without considering that data is collected at multiple sites. We choose the non-parametric Wilcoxon-Mann-Whitney test, set alpha to 0.05 and required power to 0.8. There is uncertainty concerning the effect size. Previous literature offers some guidance, however there are several important differences to our study. MI-interventions to change oral health have previously been tested on periodontist patients and patients with mental illness, populations that differ from ours. For our main variable of interest, level of plaque, these studies have found effect sizes ranging from 0.286 to 1.213¹. However, one should note that these studies have used different indexes to measure plaque, questioning the comparability of the effect sizes. Setting the power estimate to a moderate level in this range, to 0.5,

¹ An effect size of 0.286 was found after 12 weeks in Brand et al. (2012), whereas an effect size of 1.213 was found in Godard et al. (2011).

our required sample size is 106 prisoners. If we use a more conservative estimate and set it to the lowest effect size observed in the studies referred to above (0.286), the required sample size is 320.

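### Prisoners are called blind but know which treatment they received, and identical questions cannot show that a difference in self-report is a change in behaviour

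*Combined protocol and SAP*

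**What the plan says.** **Blinding of prisoners.** The Basic methodology section says "we blind prisoners from treatment status", without qualification. The Blinding section gives the reason: "Prisoners are not informed whether they are in the treatment or control group and are therefore blind to treatment status".

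**What each arm receives.** Under Intervention: "The intervention is a conversation lasting up to 30 minutes with the prisoner about his or her oral health, based on Motivational Interviewing". It adds that "the intervention included a change plan, in which the prisoner and dental staff agrees on specific behavior that the prisoner should follow". The text on follow-up under Expected timeline confines this to T0 and "only for those randomized to the treatment group". For controls the Project summary describes the examination, the questionnaire and the kit: "Both groups finally receive a toilet bag with basic equipment to regularly clean their teeth". No matched or sham conversation is described.

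**Self-reported outcomes.** Under Treatment effects and measurements: "The secondary measures of outcome are based on questionnaire responses". They cover perceptions, cleaning routines, and food and drink, which are the subjects of H2 to H4. The section describes the questions as measuring behavioural change. From the fact that they are identical at each meeting it concludes that "any difference in changes across the treatment and control group is likely to be a result of the intervention".

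**Safeguards.** The Blinding section accepts that staff may remember a prisoner's arm at T1 and T2, and answers with a second assessment of the oral examination. Nothing equivalent is described for the questionnaire.

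**The concern.** There are two separate defects.

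First, the plan claims a design property that it lacks. Withholding the name of the arm does not hide the treatment when the treatment is a conversation in which the prisoner takes part and agrees what to do.

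Second, the ground given for attributing questionnaire differences does not exclude differential reporting. A prisoner who has agreed a plan with dental staff, and later answers questions at a visit with dental staff, may answer in line with that plan whether or not he has kept to it.

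What is at stake is the reading of H2, H3 and H4. Treatment effects and measurements says questionnaire changes may matter even when the mucosal-plaque index (MPS) shows no significant change. The Project summary would treat improvement in hygiene, routines, attitude, or any combination of these as showing that the intervention works. A positive message could therefore rest on self-report alone.

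**Working it through.** **1. Does blindness follow from the plan's own text?**
- Premise in the Blinding section: prisoners are not told their group.
- Fact from Intervention and Expected timeline: one arm only has the conversation and the change plan.
- Fact from Project summary: nothing comparable is described for controls.

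Each prisoner knows whether he had the conversation. The premise supports at most that he was not told the group label. It does not support blindness to the treatment received.

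**2. Does identical wording secure the reading as behaviour?** Write the observed difference between arms in mean change from T0 as

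D = (difference in true change) + (difference in reporting shift).

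Identical questions remove differences due to wording. Adjusting for the T0 answer (Covariates) removes differences already present at T0. T0 answers are collected before the arm is revealed, so a reporting shift caused by the conversation is not in them. It arises later and in one arm only, so neither device removes the second term. Randomization makes D a causal effect on reports, but it does not separate the two terms.

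**3. The plan's own sample sizes.** Inputs from Power calculations: Mann-Whitney test, alpha 0.05, power 0.8, effect sizes 0.5 and 0.286, stated totals 106 and 320. Using asymptotic relative efficiency (ARE) 3/π for a normal parent, 1:1 allocation and the noncentral t distribution:

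| Effect size | One-sided total | Two-sided total | Plan |
|---|---|---|---|
| 0.5 | 106 | 134 | 106 |
| 0.286 | 320 | 404 | 320 |

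The method reproduces the plan's figures exactly, but only one-sided. The plan does not state sidedness; that is a separate matter.

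**4. Illustration of size.** The documents give no figure for reporting bias, so the shift b is an assumption: 0.1 to 0.2 SD in the treated arm, true effect zero, N analysed 1:1, two-sided 5% test.

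δ = b × √(N × (3/π) / 4)

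P(significant) = Φ(δ − 1.96) + Φ(−δ − 1.96)

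Example, N = 320 and b = 0.2: δ = 0.2 × √(320 × 0.9549 / 4) = 0.2 × √76.39 = 1.748. Then P = Φ(−0.212) + Φ(−3.708) = 0.416.

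| N analysed | b = 0.1 | b = 0.2 |
|---|---|---|
| 106 | 0.080 | 0.172 |
| 200 | 0.106 | 0.282 |
| 320 | 0.141 | 0.416 |
| 400 | 0.165 | 0.498 |

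Each figure is per item, against a nominal 0.05. The noncentral t gives nearly the same values (0.140 and 0.414 at 320). One-sided testing would give more: 0.22 and 0.54 at 320.

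Of these N, 106 and 320 are the plan's required totals and 400 is its working assumption of 100 in each of four prisons. 200 is added because language exclusion and attrition, for which the plan gives no rates, will reduce the analysed number.

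**The case against.** **Attribution does not rest on blinding.** A reader might infer that the plan uses the blinding claim to justify its causal reading of the questionnaires. It does not: the stated ground is that the questions are identical. This stands, and it is why the two defects are kept apart. Correcting the blinding statement would leave the attribution sentence untouched.

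**Randomization still works.** A reader might infer that no causal statement about H2 to H4 is possible. That goes too far. A difference in reported answers can be an effect of the intervention. The plan is also partly careful: H2 speaks of reported routines, part of H4 of a reported wish, and the attribution is worded as likely, not certain. But the same section describes the questions as measuring behavioural change, and that step is not secured.

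**How much prisoners know is uncertain.** The information letter is not in the documents, so whether prisoners know the hypothesis cannot be settled. The content of individual change plans is not given either, nor whether they are written down. The example questions under Intervention concern cleaning and brushing, not diet, so the overlap with the outcomes is clearest for H2. All this limits how strong a shift can be presumed. It does not restore blindness to the treatment received.

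**The numbers are illustrative.** The shift is assumed, and 320 or 400 analysed may not be reached. The smaller N are shown for that reason; the rates there are lower but still above 5%.

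**Conclusion.** The concern holds in this form. The statement that prisoners are blind is wrong as written: they are not told their group, but they know what treatment they received. Separately, the ground given for reading questionnaire differences as behavioural change is insufficient. What H2 to H4 can support is an effect on what prisoners report.

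Under an assumed pure reporting shift of 0.1 to 0.2 SD with no true effect, a two-sided 5% test is significant in 8-17% of trials at 106 analysed, 11-28% at 200, 14-42% at 320 and 16-50% at 400. These figures rest on the assumed shift, 1:1 analysis and the 3/π efficiency. They show scale and do not estimate the bias in this trial.

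A reader might also infer that the primary outcome falls with the blinding claim, or that the MPS can settle every self-reported outcome. Neither follows. The MPS is scored by examiners and has its own safeguard, though the plan itself calls that partial. It bears on oral hygiene, but it cannot arbitrate diet (H3) or perceptions (H4). H5 is counted by staff, so it raises a different question, that of staff knowledge of the arm.

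**What to change.** 1. In Basic methodology and Blinding, replace the statement that prisoners are blind with: not told their group, but aware of the treatment received.
2. In Treatment effects and measurements, limit the attribution sentence to reported outcomes. State that differences in H2 to H4 may reflect differential reporting, and that a change in cleaning or dietary behaviour will not be concluded from self-report alone.
3. Claim improved oral hygiene only with support from the MPS, noting that its two-assessor safeguard is itself partial.
4. For H4, where self-report is the construct being measured, give the response-bias caveat and do not require confirmation by the MPS.

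These are changes of wording and interpretation, with no new data or sample. The cost is that the permitted conclusions for H2 to H4 become more modest.

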Dental staff also take note about how many times the prisoner ask questions about their findings from the oral examination. If the intervention raises their awareness to oral health, it is likely that those in the intervention group ask more questions during the follow-up period. Hence, this is also a secondary variable of interest.

We choose not to include questions about what sort of criminal offence the prisoner had committed and related questions that could challenge dental staffs perceived safety. For example, knowing you are talking to a sexual offender or murderer is likely to affect our dental staff negatively. When the prisoner signs the consent to participate in the study, he also approves that we are allowed to collect such data from the Norwegian Correctional Service. However, we are still not sure whether they will gain us access to such administrative data.

Randomization:

Randomization is done using the randomization tool www.randomizer.org. We randomize prisoners in the order that we receive lists of prisoners who have signed up to participate. Although this order

may not be random, the randomization process ensures that assignment to treatment and control group is. We block on prison level, to ensure a balance between treatment and control group in each prison. To ensure that there is not, by chance, an unequal assignment into treatment or control, we force the randomization to balance assignment into treatment and control for every fourth prisoner. That is, in groups of four, if the first two are assigned to the treatment group, the next two will be control group. To reduce the likelihood that dental staff in prison could guess the assignment of the next prisoner, we used every fourth prisoner rather than every second prisoner. The order that the prisoners meet may not be the same order as we randomize, further ensuring that dental staff may not guess whether the next prisoner is in the treatment group or not.

It would be very interesting to stratify the sample on gender, however we expect at most only to have a few observations on female prisoners. From early 2022, female prisoners will serve time outside of Rogaland County.

The unit of observation is at individual level. To ensure privacy of the prisoners, we do not collect any information that directly identifies them. However, given the detailed questionnaire, we do collect data that contains identifiable information.

Blinding:

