As mentioned under the section for blinding, there will be two assessments of the MPS index score at T1 and T2, as dental staff are not blind to their second and third meeting with the prisoner. If the original examiner finds no improvement in the MPS-index score, the second examiner's score will be ignored. If the original examiner finds an improvement, the average score of the original examiner and the second examiner will be used, however the second examiner's score will not be used to increase the average score above the assessment of the original examiner. We consider this a conservative approach. If the original examiner is not part of the team that evaluates at T1 and T2 (for example if the prisoner has been transferred to a different prison, or due to sick absence), an average score of the two assessments by the new examiners will be used.

Another concern is potential differences in how oral examinations and the intervention is conducted across multiple sites. To minimize differences, all dental staff have undergone the same MI training and practice. All oral examinations are being conducted by trained professionals, and they have gone through a calibration day prior to the start of the data collection. Moreover, they will continuously be provided guidance from a professional MI-consultant. In addition, we track the time they spend on each MI-based conversation.

Recruitment of prisoners may also be slightly different from one prison to another, as in half of the prisons it is done by prison officers and the other half it is done by dental staff. Prisoners may perceive the question of whether they want to participate or not differently, depending on whether they are asked by a prison officer compared to a dental staff. Moreover, the language assessment may also be different. Although this occurs independent of the randomization, it might lead to a difference in the population recruited to the experiment across prisons. Unfortunately, we could not have the same recruiter across all prisons. However, the information provided to the prisoners is the same across all prisons. This also applies to the instructions concerning language assessment; in the case of uncertainty about Norwegian language skills, the same screening question is asked across prisons, and the same evaluation criteria is being used.

Conclusion

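### At T1 and T2 the two-assessor safeguard covers only the MPS examination, so the staff-made H5 question count is open to observer bias; for the H2–H4 questionnaire the risk depends on details the plan does not state

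*Combined protocol and SAP*

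**What the plan says.** **Knowledge of the arm.** Under Blinding, T0 data are collected before the arm is revealed. The section accepts that once "prisoners are back at T1 and T2 for follow-up oral examinations and questionnaires, dental staff might still remember whether the prisoner was treated". The plan's response is that "there are two independent assessments of this at T1 and T2", meaning the oral examination. Other issues is firmer. It provides for "two assessments of the MPS index score at T1 and T2, as dental staff are not blind to their second and third meeting". Basic methodology frames the safeguard the same way: staff are blind when examining, "or the oral examination is conducted by two dental staff independently of each other".

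**The H5 outcome.** Three sections describe it:
- Hypothesis (H5) predicts an "increase in number of questions the prisoner asks during their visit with the dental staff".
- Treatment effects and measurements says "dental staff take notes of how many times the prisoner asks questions about his teeth".
- Data collection and sources of data says "Dental staff also take note about how many times the prisoner ask questions about their findings from the oral examination", and expects that "those in the intervention group ask more questions during the follow-up period".

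**The H2–H4 outcomes.** These come from the questionnaire. Data collection and sources of data gives data collection to trained dental staff and lists questionnaire answers among the sources. For the wording of the questions, the plan refers to the questionnaire form, which is not among the documents.

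**Interpretation.** Treatment effects and measurements attributes a between-arm difference in changes in the questionnaire outcomes to the intervention as the likely cause. It adds that such changes may matter even if MPS does not move.

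**The concern.** H5 is an observer's tally. The person making it may have held the MI session with that prisoner, may remember doing so, and can know that more questions are expected in the treated arm. Deciding whether a remark is a question, and whether it is about the right subject, takes judgement, and three unreconciled descriptions widen that judgement. The plan recognised this problem for MPS and protected MPS against it, but did not extend the protection to H5.

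At stake is what a positive secondary result would mean. H2–H5 are four of the five hypotheses. The Project summary would regard the intervention as effective if it improves hygiene, routines and/or attitude, so secondary results alone could carry a conclusion. An H5 difference might be read as greater curiosity when part of it reflects who counted. The same would apply to H2–H4 if the person who held the MI session and agreed the change plan also put the follow-up questions in person.

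**Working it through.** The plan gives no figure for this point, so the check is a comparison of sections and a short piece of algebra.

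**Step 1. Coverage of the safeguard by outcome at T1 and T2**

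| Outcome | Recorded by | Second assessment planned? |
|---|---|---|
| H1, MPS | Dental staff | Yes (Basic methodology, Blinding, Other issues) |
| H5, question count | Dental staff (Treatment effects and measurements; Data collection) | None described |
| H2–H4, questionnaire | Collected by dental staff (Data collection); mode and individual not stated | None described |

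**Step 2. What is counted for H5**
- Hypothesis: questions during the visit, with no limit on subject.
- Treatment effects and measurements: questions about his teeth.
- Data collection: questions about the examination findings, the narrowest of the three.

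A question about toothbrushing, for example, fits the first two descriptions but not clearly the third.

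**Step 3. Whether the T0 covariate helps.** Let *t* be the true effect on the count and *b* the average extra count recorded in the treated arm at follow-up because the recorder knows the arm. T0 is collected blind, so the expected between-arm difference at T0 is 0.
- Direct comparison at T1: *t* + *b*.
- Difference in changes: (*t* + *b*) − 0 = *t* + *b*.
- Comparison adjusted for baseline with slope *r*: (*t* + *b*) − *r* × 0 = *t* + *b*.

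The Mann-Whitney tests make the first comparison. The regressions with the pre-treatment value (Covariates) and the individual fixed-effects models (Statistical model specification) rest on the other two ideas. The algebra is on the mean scale, but the reason is general: *b* is absent from the T0 value, so conditioning on T0 cannot remove it.

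**Step 4. Whether a size can be given.** No document gives the mean count, its distribution, the number analysed or *b*. A simulation with assumed inputs shows how far the answer depends on them. Take 160 analysed (an assumed 40% of 4 × 100 = 400), no true effect, Poisson or negative binomial counts, a two-sided 5% Mann-Whitney test, and one extra question recorded in some treated visits.

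| Assumed mean count | Extra question in 10% of treated visits | In 20% |
|---|---|---|
| 1 to 4 | 5–9% false positives | 7–22% |
| 0.3 | about 19% | about 55% |

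With no extra recording the rate stays near 5%. Changing only the assumed mean moves the result several-fold, so these figures show sensitivity and are not an estimate for this trial.

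**The case against.** **The plan already discloses the weakness.** In part it does: the Blinding sentence names the follow-up questionnaires alongside the examinations. What is missing is a remedy for anything beyond MPS, and a caveat where the plan says how differences will be read.

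**The definition point is small.** That is fair. H5 in the Hypothesis section is a general statement, Treatment effects and measurements moves between teeth and oral health, and one sentence would align the three. No recording form or staff instruction is available, so loose counting in practice is an inference. It matters mainly because it adds to an unblinded count.

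**Prisoners are blind, and these outcomes are secondary.** Prisoner blinding does not address bias that comes from the recorder. Secondary status limits the seriousness but does not remove the problem.

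**The original examiner is not always present.** Other issues provides for transfer and sick absence, so exposure varies between visits.

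**Stronger readings that the documents do not support**
- *The plan leaves open who collects the questionnaire.* It does not: Data collection names trained dental staff. Only the mode and the individual at follow-up are unstated.
- *The H2–H4 answers are biased by the MI provider.* This would need that person to administer the follow-up questionnaire in a way that allows influence. The text does not say so, and the questionnaire form may settle the mode.
- *A bias of known size exists.* The documents show an opening for bias, not that it occurred.

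**Conclusion.** The concern holds for H5. The recorder may know the arm, the only safeguard is confined to MPS, and neither prisoner blinding nor the T0 value removes a recording bias that begins at follow-up. The three descriptions of the count should be reconciled. For H2–H4 the risk is conditional: the answers are collected by the same staff group, but whether the arm could influence them depends on a mode and a person that the available text does not give.

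The size is not estimable from the documents. The primary outcome is not affected by this point. The conclusion assumes that the second assessment is used only as described in Basic methodology, Blinding and Other issues, and that no separate staff instruction already protects the count. The matter should be corrected because the remedy is cheap and the affected outcomes may support a claim of effectiveness.

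**What to change.** 1. **Recorder.** At T1 and T2, the examiner already planned for the second MPS assessment, who did not hold that prisoner's T0 session and is not told the arm, records the H5 count and handles the questionnaire, in the same way in both arms.
2. **Definition and window.** Use one written H5 definition and one counting window at T0, T1 and T2, reconciling the three descriptions. One option is every question about the prisoner's own teeth, oral health or examination findings, from arrival to the end of the examination and questionnaire. At T0 that window closes before the arm is revealed. Keep the questionnaire mode the same as at T0. A window or mode changed only at follow-up would mean that the T0 value is no longer the equivalent pre-treatment observation that Covariates relies on.
3. **Log.** Record who made the count and who handled the questionnaire at each visit, and mark visits completed under the old arrangement.
4. **Interpretation.** Qualify Treatment effects and measurements: for self-reported and staff-counted outcomes, a difference in changes may also reflect who asked or who recorded.

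**Cost.** No new role is needed, but the second examiner spends somewhat longer at each visit, and Expected timeline lists time per prisoner among the limits on recruitment. If that time cannot be found, items 2 to 4 need only text and a small addition to the record form.

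**Limits.** The plan calls the two assessments independent but nowhere says the second examiner is blind, and a prisoner may mention the MI session. The bias is therefore reduced, not removed. Data collection had already begun when the plan was written, so completed visits keep the old arrangement.
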